8.3.7 Four-week Continuous Abstinence Rate Using Exhaled Carbon Monoxide Level

Endpoint calculation:

- If subject has exhaled CO level of less than 5 ppm using the Vitalograph Breath CO monitor in the office at scheduled Week 5 and Week 7, then set it as four-week continuous abstinence.
 - Missing value check:
 - For CO value, both Week 5 and Week 7 value are not missing.
- All the others will be set as non-abstinent.
 - Week 5 or Week 7 CO value is missing.
 - Lost to follow-up/Early termination
 - Subjects with adequate data that they were smoking

A descriptive statistic will be provided with 90% binomial confidence intervals.

For all binomial confidence intervals, it is based on normal approximation. If the number of abstinent or the number of non-abstinent ≤ 5 , we will use the exact method.

8.3.8 Four-week Continuous Abstinence Rate Using Self-report

Endpoint calculation:

- If there is no smoking in the self-report, then set it as four-week continuous abstinence.
 - Missing value check:
 - For self-report value, only one missing value in every visit week (7 days) is allowed.
- All the others will be set as non-abstinent.

Protocol 405-201-00055 Statistical Analysis Plan

- There are two or more missing in Self-report every visit week (7 days)
- Lost to follow-up/Early termination
- Subjects with adequate data that they were smoking

A descriptive statistic will be provided with 90% binomial confidence intervals.

For all binomial confidence intervals, it is based on normal approximation. If the number of abstinent or the number of non-abstinent ≤ 5 , we will use the exact method.

8.3.9 Summary of CO Level

The baseline for CO level analyses is defined as the last evaluable assessment prior to first IMP. The summary statistics for changes from baseline in the CO level will be provided. The incidences and percentage of subjects with CO level greater than or equal to 5 PPM will be summarized.

8.3.10 Number of Cigarettes Daily

The summary statistics for changes from baseline in the average number of cigarettes smoked per day will be provided.

9 Safety Analyses

Safety assessments including AEs, vital signs, ECGs, clinical laboratory tests (serum chemistry, hematology, and urinalysis) will be summarized for the Safety Analysis Set.

In summarizing the incidence of clinically relevant abnormalities in clinical laboratory results, vital sign measurements and ECG measurements, a subject must have had an evaluation that meets the specified criteria. For clinical laboratory results and ECG measurements, incidence rate will be calculated as the number of subjects having at least one abnormality divided by the number of subjects in the Safety Analysis Set. For vital sign measurements, incidence rate will be calculated as the number of subjects having at least one abnormality divided by the number of subjects in the Safety Analysis Set.

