There are currently seven Food and Drug Administration (FDA)-approved smoking cessation medications, which fall into three main categories: nicotine replacement therapy (NRT) including nicotine patch, gum, lozenge, inhaler, and nasal spray; varenicline (Chantix); and bupropion (Zyban/Wellbutrin). Among US smokers, 29.1% use NRT when attempting to quit smoking whereas only 7.9% use varenicline and 2.4% use bupropion.^{8,9} Two other medications that show some efficacy, clonidine and nortriptyline, are not FDA approved, and account for less than 1% of smoking cessation treatment.¹⁰ None of the current treatments yields sustained abstinence rates of over 25% at one year, but varenicline is the most efficacious. Varenicline is a full agonist on $\alpha 7$ -nicotinic acetylcholine receptors (nAChRs) and a partial agonist on the $\alpha 4\beta 2$, $\alpha 3\beta 4$, and $\alpha 6\beta 2$ subtypes.^{2,11,12} Smoking abstinence rates at weeks 9-12 in two Phase III trials of varenicline were nearly identical at 44%. Given that four-week continuous abstinence at weeks 4-7 will be taken to be the primary abstinence outcome in the present study, and modeling relapse curves over the initial weeks of abstinence suggests that abstinence rates are ~5% higher at 6 weeks than at 12 weeks after the target quit-smoking date,¹³ in this study a slightly higher rate of 50% abstinence will be taken to be the benchmark criterion to meet or exceed. Common adverse events associated with varenicline include nausea, insomnia, abnormal dreams, headaches, and nasopharyngitis.¹⁴ The most common adverse reaction reported is nausea, with 30-40% of participants in randomized control trials reporting mild to moderate levels of nausea.¹⁵ Discontinuation/drop-out rates of nearly 10% have been noted during clinical trials due to these adverse effects.¹⁶ In real-world settings, discontinuation of varenicline treatment may be as high as 57%.⁸

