6.6.6 Final Study Visit (V6) – 7 weeks on IMP

Seven weeks (\pm 3 days) after starting the study drug, participants will return to the Center for V6 to complete questionnaires and assessments. Participants will also be asked to return all unused IMP.

The sequence of the following questionnaires and assessments will be at the discretion of the Investigator (or designee).

6.6.6.1 **Questionnaires**

- Other Nicotine Use Questionnaire
- Modified Shiffman-Jarvik Withdrawal Scale
- Modified Cigarette Evaluation Questionnaire Extended (mCEQE)
- Minnesota Withdrawal Questionnaire
- Fagerström Test for Nicotine Dependence

6.6.6.2 **Assessments**

- Review of Concomitant Medication
- Review of Concomitant Disease
- Expired air CO breath test
- Alcohol breath test
- Urine collection for urinalysis and pregnancy (all participants with the potential to become pregnant)
- Blood collection for safety laboratory testing, pharmacokinetics, and future biospecimen research (for those participants who consented to this optional collection)
- Vital signs (systolic and diastolic blood pressure, pulse rate, and respiratory rate), will be measured in sitting position after the participant has rested for at least 5 minutes.
- Weight
- Temperature
- Electrocardiogram (ECG) -- A standard 12-lead ECG will be recorded after the participant has rested for at least 5 minutes in a supine position.
- Columbia-Suicide Severity Rating Scale (C-SSRS)
- Review of adverse events (as needed)

- Physical examination (as needed)

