3.3 Trial Population

The study population includes 50 cigarette smoking adults. Smokers between 21 and 65 years of age (inclusive), 18 to 40 kg/m² (inclusive) of body mass index(BMI), with no restriction on gender, race and ethnicities, or social-economic status, and have smoked an average of at least 10 commercially available cigarettes per day for the last 12 months will be screened. Subjects who have an expired air carbon monoxide (CO) reading of at least 10 ppm at screening, express a desire to quit smoking within the next 30 days, and own a smart phone with text message and data capabilities compatible with necessary surveys will be eligible for inclusion.

4 Sample Size

This is a single-arm trial to assess the effect of centanafadine for a four-week continuous smoking abstinence rate during Week 4 to Week 7.

[Table 4-1](#) shows the 90% confidence interval for 50 subjects when the four-week continuous smoking abstinence rate is 0.3, 0.4, 0.45 and 0.5.¹

Table 4-1 90% Confidence Interval for Sample Size of 50 Subjects						
Confidence Level	Sample Size	Actual Width	Proportion	Lower Limit	Upper Limit	
0.9	50	0.22885	0.3	0.19488	0.42373	
0.9	50	0.24299	0.4	0.28313	0.52612	
0.9	50	0.24639	0.45	0.32912	0.5755	
0.9	50	0.24751	0.5	0.37625	0.62375	

Lower limit and upper limit are 90% confidence interval of the proportion given the sample size and proportion of four-week continuous smoking abstinence.

Protocol 405-201-00055 Statistical Analysis Plan

5 Statistical Analysis Datasets

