5.2 Safety Analysis Set (SAS)

Safety Analysis Set includes all subjects who are administered at least one dose of IMP, regardless of any protocol violation.

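### Abnormal laboratory, ECG and vital-sign rates are divided by everyone dosed, so a participant with no post-baseline reading is in effect counted as not abnormal

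*SAP*

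**What the plan says.** SAP section 9 gives the denominator twice, once for laboratory results and ECG and once for vital signs, in the same terms: "the number of subjects having at least one abnormality divided by the number of subjects in the Safety Analysis Set". SAP section 5.2 defines that set: "Safety Analysis Set includes all subjects who are administered at least one dose of IMP, regardless of any protocol violation". Having a post-baseline evaluation is not a condition of membership.

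The same paragraph of SAP section 9 opens by saying that "a subject must have had an evaluation that meets the specified criteria". This settles who counts as abnormal. It does not alter the two denominator sentences that follow it.

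SAP section 5.5 says that missing data are not imputed. SAP sections 9.4 and 9.6 count unscheduled as well as scheduled post-baseline readings for vital signs and ECG.

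On timing, the Protocol's V6 assessments (6.6.6.2) include "Electrocardiogram (ECG) -- A standard 12-lead ECG will be recorded". The Schedule of Events (Protocol 6.8) shows the only other ECG at screening.

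**The concern.** A participant who takes one dose and leaves before a parameter is measured contributes nothing that could be abnormal, yet adds one to the denominator. The table then treats not measured in the same way as measured and not abnormal. That sits awkwardly beside the no-imputation rule.

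Three features of this trial make it worth attention:

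- There is one arm. No control group carries the same dilution, so readers have only the absolute rate.
- Some parameters are measured late and once. Someone who leaves before Week 7 has no scheduled on-treatment ECG or urinalysis.
- The Schedule of Events has no early-termination visit, Protocol 4.6 lists no assessments at discontinuation, and the safety follow-up (Protocol 6.6.8) is a telephone contact.

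What is at stake is how the abnormality tables CT-10.1, CT-11.1 and CT-12.1 are read. The primary abstinence endpoint is not affected.

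**Working it through.** **Is there a figure in the plan to reproduce?** No. Neither document states an expected abnormality rate, a precision target or a drop-out assumption for these tables. SAP Table 4-1 concerns the abstinence rate only.

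**Inputs**

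- N = 50, from SAP 3.3: "The study population includes 50 cigarette smoking adults". I assume that all 50 are dosed.
- x = number of participants with at least one qualifying abnormality. I take x = 3 as an illustration.
- m = number of dosed participants with no post-baseline reading of the parameter. The documents do not give it, so I show a range from 0% to 40% of N.

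**Formulas**

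- Rate under SAP section 9: x / N
- Rate among those measured: x / (N − m)
- Ratio of the first to the second: (N − m) / N

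**Results for N = 50 and x = 3**

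| Without a reading | m | Measured | Rate under SAP 9 | Rate among measured | Ratio |
|---|---|---|---|---|---|
| 0% | 0 | 50 | 3/50 = 6.0% | 3/50 = 6.0% | 1.00 |
| 10% | 5 | 45 | 3/50 = 6.0% | 3/45 = 6.7% | 0.90 |
| 20% | 10 | 40 | 3/50 = 6.0% | 3/40 = 7.5% | 0.80 |
| 40% | 20 | 30 | 3/50 = 6.0% | 3/30 = 10.0% | 0.60 |

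The ratio does not depend on x. The direction is fixed: whenever m > 0 and x > 0, the reported rate is below the rate among those measured.

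**Where m can be large**

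| Parameter | Scheduled on-treatment readings | Who has no scheduled reading |
|---|---|---|
| ECG, urinalysis | V6 only | Anyone leaving before Week 7 |
| Chemistry, hematology | V4 and V6 | Anyone leaving before Week 3 |
| Vital signs | V3, V4, V5, V6 | Anyone leaving before about Week 1 |

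The timings are from Protocol 6.6.3 to 6.6.6 and 6.8 and from SAP 9.3. Unscheduled vital-sign and ECG readings count, so m can be smaller than the schedule alone implies.

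**A related case.** SAP Appendix 2 has criteria for uric acid, creatine phosphokinase and fasting lipids, which are not in the Protocol's chemistry panel (Table 1). If rows for these were produced under the stated rule with no such tests done, they would read 0/50, where the accurate entry is that the test was not assessed.

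**The case against.** The strongest reply is that the planned rate is a properly defined quantity: the proportion of dosed participants with an observed abnormality. The tables are descriptive, no decision rule uses them, abnormal values are also listed by subject, and CT-1.3 reports completion by week. A careful reader could partly recover who was not evaluated. This stands as a limit on the weight of the point. It does not justify leaving the evaluated n off the row.

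A reader might infer that the rates will be heavily diluted by taking m from the Protocol's background section, which says that "Discontinuation/drop-out rates of nearly 10% have been noted during clinical trials" and that "discontinuation of varenicline treatment may be as high as 57" per cent. The documents do not support that. Both figures concern varenicline; the first is discontinuation because of adverse effects and the second is from real-world use. Neither is the share of participants in this trial without a reading, and stopping a drug is not the same as having no reading.

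A reader might also infer that all safety rates suffer alike. They do not. For blood pressure, only someone who leaves before V3 with no unscheduled reading is affected. Nor is it shown that the loss is worst among those leaving with side effects. They may well be tested: Protocol 6.5 allows extra blood and urine samples, and unscheduled ECGs and vital signs count.

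Missing baselines should add little. Laboratory tests and ECG are needed for eligibility, vital signs are taken at V1 and V2, and most Appendix 2 criteria are absolute.

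Finally, it is tempting to argue from the upper confidence limit when no events are seen. The SAP plans no confidence limits for these rates, so that argument addresses no planned analysis.

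**Conclusion.** The point holds in a conditional form. As written, SAP section 9 understates the abnormality rate among those measured by the factor (N − m)/N for each parameter. With 50 dosed and 3 abnormal, the reported 6.0% corresponds to 6.7%, 7.5% or 10.0% of those measured if 10%, 20% or 40% lack a reading, and to 6.0% if none do. These percentages are assumptions, because the documents give no figure for this trial.

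The potential effect is largest for ECG and urinalysis, smaller for chemistry and hematology, and smallest for vital signs. The documents do not show that any particular degree of dilution will occur. They show only that the rule produces it whenever a reading is missing and at least one abnormality is seen. The point should be corrected because the trial has a single arm and the correction is cheap, but it bears on descriptive safety tables only.

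Changing the denominator should not be read as removing bias. If those who leave are more likely to be abnormal, the rate among those measured is also too low for the dosed population; selective unscheduled testing could push it the other way. What the change gives is a correct rate for those measured, with a visible count of how many that is.

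**What to change.** In SAP section 9, and for CT-10.1, CT-11.1 and CT-12.1:

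- Define the denominator for each parameter as the Safety Analysis Set participants with at least one post-baseline evaluation of that parameter and, where the criterion requires a change, a baseline value as well.
- Print that n in each row.
- Reword the opening sentence of the paragraph so that it plainly describes the numerator and cannot be taken as a rule about the denominator.
- Keep the full-set rate as a supplementary column if wanted, labelled as the proportion of dosed participants with an observed abnormality.
- Add a sentence saying that the evaluable denominator does not correct for informative drop-out.

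The cost is a wording change in the SAP and minor programming in three tables. No new data are needed. Where readings are missing, non-zero rates will look slightly less favourable.

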9.1 Extent of Exposure

Number of subjects who were administered IMP will be summarized by duration of exposure and descriptive statistics (mean, maximum, and minimum) of daily dose will be calculated and summarized for safety analysis set.

9.2 Adverse Events

All AEs are coded using Medical Dictionary for Regulatory Activities (MedDRA). A TEAE is defined as an AE which starts after start of first IMP or an AE continues from

Protocol 405-201-00055 Statistical Analysis Plan

baseline of the specific corresponding duration and was serious, trial drug-related or results in death, discontinuation, interruption or reduction of IMP.

The incidences of the following TEAEs will be reported:

- TEAEs
- TEAEs by severity
- Potentially drug-related TEAEs
- TEAEs with an outcome of death
- Serious TEAEs
- Discontinuations due to TEAEs
- Treatment-emergent adverse events of special interest (AESI) related to **CCI**
[REDACTED]
- TEAEs related to Abuse-Potential

9.3 Clinical Laboratory Data

Hematology and serum chemistry will be collected at screening visit, Week 3 visit and Week 7 visit. Urinalysis will be collected at screening visit and Week 7 visit. The baseline for laboratory analyses is defined as the last evaluable assessment prior to first IMP. The summary statistics for changes from baseline in the clinical laboratory measurements will be provided. The incidences and percentage of potentially clinically relevant laboratory tests abnormalities will be summarized. The potentially clinically relevant laboratory test abnormalities will be listed by subject and by test. The criteria for Identifying Laboratory Values of Potential Clinical Significance are provided in [Appendix 2](#). Potential Hy's law cases will be displayed in a listing. The laboratory results for serum chemistry, hematology, and urinalyses will be listed.

If laboratory tests assessments are repeated for the same visit window, the last repeated values will be used for summary tables. This is accomplished by sorting patient data by visit date and visit time (if applicable) within same visit window. If the lab data are recorded as ranges (i.e., including < or > limit of quantification), these data are not included in the calculations for changes from baseline but included in the calculations for incidences.

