10.	Participants that have a positive alcohol test (via breathalyzer or blood), a positive drug screen for illicit drugs (Table 6.3.5) at screening or baseline. NOTE: Participants who test positive for marijuana at screening may be enrolled if they have no evidence of a substance use disorder and if they agree to refrain from use for the duration of the trial.
11.	Any participant who has any other medical or physical condition(s) that, in the opinion of the investigator, may prevent the participant from completing the trial or would go against the participant's best interest with participation in the trial. This would include any significant illness or unstable medical condition that could lead to difficulty complying with the protocol.

Exclusion Criteria	
12.	
The following laboratory test and ECG results are exclusionary:
 
 1) Platelets \leq 75,000/mm³ 2) Hemoglobin \leq 9 g/dL 3) Neutrophils, absolute \leq 1000/mm³ 4) AST $>$ 2 \times upper limit of normal 5) ALT $>$ 2 \times upper limit of normal 6) Creatinine \geq 2 mg/dL 7) HbA1c \geq 7% 8) QTcF $>$ 450 msec for males or $>$ 470 msec for females 
NOTE: In addition, participants should be excluded if they have any other abnormal laboratory tests, vital sign results, or ECG findings which in the investigator's judgment are medically significant and that would impact the safety of the participant or the interpretation of the trial results.

13.	Participants with a history of prior exposure to centanafadine.
14.	Use of smokeless tobacco (chewing tobacco, snuff), cigars (except for "Black & Mild" cigars or Cigarillos), pipes, hookah, e-cigarettes, nicotine replacement therapy or other smoking cessation treatments (e.g., bupropion as Zyban, or varenicline) within 14 days of screening.
15.	Participants who participated in a clinical trial and were exposed to interventional trial medication within the last 30 days prior to screening or who participated in more than 2 interventional clinical trials within the past year.

ALT = alanine aminotransferase; AST = aspartate aminotransferase; CBP = childbearing potential; HbA1c = glycosylated hemoglobin; QTcF = QT interval corrected for heart rate by the Fridericia formula.

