Orthostatic Hypotension	≥ 30 mmHg decrease in systolic blood pressure or a ≥ 20 mmHg in diastolic blood pressure after at least 3 minutes of standing compared to the previous supine blood pressure.	Not Applicable (baseline status not considered)
Orthostatic Tachycardia	≥ 25 bpm increase in heart rate from supine to standing	Not Applicable (baseline status not considered)
Weight	-	≥ 7% increase ≥ 7% decrease

a In order to be identified as potentially clinically relevant, an on-treatment value must meet the “Criterion Value” and also represent a change from the subject’s baseline value of at least the magnitude shown in the “Change Relative to Baseline” column.

b As defined in “Supplementary Suggestions for Preparing an Integrated Summary of Safety Information in an Original NDA Submission and for Organizing Information in Periodic Safety Updates,” FDA Division of Neuropharmacological Drug Products draft (2/27/87).

Protocol 405-201-00055 Statistical Analysis Plan

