Appendix 2 Criteria for Identifying Laboratory Values of Potential Clinical Relevance

Laboratory Tests		Criteria
Chemistry		
AST (SGOT)		$\geq 3 \times$ upper limit of normal (ULN)
ALT (SGPT)		$\geq 3 \times$ ULN
Alkaline phosphatase		$\geq 3 \times$ ULN
BUN		≥ 30 mg/dL
Creatinine		≥ 2.0 mg/dL
Uric Acid		
Men		≥ 10.5 mg/dL
Women		≥ 8.5 mg/dL
Bilirubin (total)		≥ 2.0 mg/dL
Creatine Phosphokinase (CPK)		$> 3 \times$ ULN
Hematology		
Hematocrit		
Men		$\leq 37\%$ and decrease of ≥ 3 percentage points from Baseline
Women		$\leq 32\%$ and decrease of ≥ 3 percentage points from Baseline
Hemoglobin		
Men		≤ 11.5 g/dL
Women		≤ 9.5 g/dL
White blood count		$\leq 2,800/\text{mm}^3$ or $\geq 16,000/\text{mm}^3$
Eosinophils		$\geq 10\%$
Neutrophils		$\leq 15\%$
Absolute neutrophil count		$\leq 1,500/\text{mm}^3$
Platelet count		$\leq 75,000/\text{mm}^3$ or $\geq 700,000/\text{mm}^3$
Urinalysis		
Protein		Increase of ≥ 2 units
Glucose		Increase of ≥ 2 units
Additional Criteria		
Chloride		≤ 90 mEq/L or ≥ 118 mEq/L
Potassium		≤ 2.5 mEq/L or ≥ 6.5 mEq/L
Sodium		≤ 126 mEq/L or ≥ 156 mEq/L
Calcium		≤ 8.2 mg/dL or ≥ 12 mg/dL
Glucose		
Fasting		≥ 100 mg/dL
Non-Fasting		≥ 200 mg/dL
Total Cholesterol, Fasting		≥ 240 mg/dL
LDL Cholesterol, Fasting		≥ 160 mg/dL
HDL Cholesterol, Fasting		
Men		< 40 mg/dL
Women		< 50 mg/dL
Triglycerides, Fasting		≥ 150 mg/dL

Protocol 405-201-00055 Statistical Analysis Plan

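### The SAP's laboratory-abnormality table can count eligible participants whose haemoglobin, neutrophils or other values were already flagged at entry and have not changed

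*SAP*

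**What the plan says.** **Entry.** Protocol 4.3, exclusion 12, opens with "The following laboratory test and ECG results are exclusionary". It removes haemoglobin of 9 g/dL or less (both sexes) and absolute neutrophils of 1000/mm³ or less. It also sets limits for platelets, AST, ALT, creatinine and HbA1c. A note extends the exclusion to other abnormal results "which in the investigator's judgment are medically significant" and that would affect safety or the interpretation of the trial.

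**Flagging.** SAP Appendix 2 flags haemoglobin at 11.5 g/dL or less (men) or 9.5 g/dL or less (women), and "Absolute neutrophil count" at 1,500/mm³ or less. None of these entries carries a change condition. Haematocrit, in the same table, also requires a fall of at least 3 percentage points from baseline, and the two urinalysis items are defined as increases.

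**Counting.** The opening text of SAP 9 requires only that "a subject must have had an evaluation that meets the specified criteria". The incidence is the number of participants with one or more abnormalities over the whole Safety Analysis Set. SAP 9.3 then states that "The incidences and percentage of potentially clinically relevant laboratory tests abnormalities will be summarized" (table CT-10.1). It defines a laboratory baseline, the last usable value before the first dose, but uses it only for change from baseline.

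**The concern.** The entry range and the flagging range overlap, and the counting rule does not separate values that were there before treatment from values that arose on it. A man who enters at 11.0 g/dL, or anyone who enters at 1300/mm³, satisfies the protocol and also satisfies Appendix 2 before taking a tablet. If the value stays the same at Week 3 and Week 7, the participant still qualifies for CT-10.1. On the literal wording the screening value alone would be enough.

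The trial has one group, so no control column shows how often such values occur without the drug. Within CT-10.1 a reader cannot tell carried-in values from new ones. With about 50 participants, one or two people visibly move a percentage.

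**Working it through.** The documents give no figure on this point to reproduce. The check compares the two sets of limits and then works out the effect on an incidence.

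**Step 1. Entry range against flag.** Protocol 6.5.1 and 6.5.2 schedule chemistry and haematology at screening, V4 and V6. The screening value is therefore normally both the eligibility value and the SAP's laboratory baseline, and the two limits apply to the same measurement.

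| Test | Admitted by exclusion 12 | Flagged by Appendix 2 | Eligible and already flagged |
|---|---|---|---|
| Haemoglobin, men | above 9 g/dL | 11.5 g/dL or less | above 9 to 11.5 (width 2.5 g/dL) |
| Haemoglobin, women | above 9 g/dL | 9.5 g/dL or less | above 9 to 9.5 (width 0.5 g/dL) |
| Absolute neutrophils | above 1000/mm³ | 1,500/mm³ or less | above 1000 to 1500 (width 500/mm³) |
| Platelets, low | above 75,000/mm³ | 75,000/mm³ or less | none |
| Platelets, high | no limit | 700,000/mm³ or more | whole flagged range |
| Creatinine | below 2 mg/dL | 2.0 mg/dL or more | none |
| AST, ALT | up to 2 × ULN | 3 × ULN or more | none |
| Bilirubin, BUN, alkaline phosphatase, white cells, eosinophils, sodium, potassium, chloride, calcium | no numeric limit | flagged, no change condition | whole flagged range |

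**Step 2. Counting rule across the safety sections.**

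- SAP 9.4 (vital signs) and 9.6 (ECG) both refer to post-baseline visits when describing the incidence. SAP 9.3 does not.
- Footnote a of Appendix 1 begins "In order to be identified as potentially clinically relevant, an on-treatment value must meet the" and goes on to require a change from baseline. Appendix 3 carries the same footnote. Appendix 2 has none.
- Reading 9.3 as limited to post-dose values would remove the screening value from the count. It would not remove a stable 1300/mm³ measured again at Week 3 or Week 7.

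**Step 3. Effect per participant.** Assume all 50 planned participants are dosed. Then *k* carried-in participants add k/50 to that test's incidence: 0 add 0%, 1 adds 2%, 2 add 4%, 3 add 6%.

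**Step 4. How likely is at least one?** The documents give no prevalence *p* of an eligible value that is already flagged, so these are assumed values. Expected number = 50p; P(at least one) = 1 − (1 − p)^50.

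| Assumed p | Expected number | P(at least one) |
|---|---|---|
| 0.5% | 0.25 | 22% |
| 1% | 0.5 | 39% |
| 2% | 1.0 | 64% |
| 5% | 2.5 | 92% |

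**Step 5. Why the denominator matters in the fix.** As an illustration, suppose 2 of 50 are flagged at baseline and stay flagged, and 1 other becomes flagged on treatment. The current rule gives 3/50 = 6.0%. Removing the two from the numerator only gives 1/50 = 2.0%. Using those at risk gives 1/48 = 2.1%, with 2/50 = 4.0% shown separately. The differences are small here, but only the last form keeps both facts visible.

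**The case against.** The strongest reply is that this is a descriptive table with no test, threshold or decision attached, and that other planned outputs show baseline status. These are mean changes from baseline (CT-10.2.1 to CT-10.2.3), shift tables (CT-10.2.5 to CT-10.2.7) and listings of flagged values by subject and by test (CT-10.3.1, CT-10.3.2). With about 50 people, every flagged participant can be checked by hand. The note to exclusion 12 also lets the investigator keep out medically significant abnormalities.

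Much of this stands, and it lowers the priority. It does not remove the problem. The note is discretionary and leaves the bands in Step 1 open. The SAP does not say that the shift tables use the Appendix 2 limits, so new-onset incidence may not be recoverable from them. The listings do not change what CT-10.1 reports.

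A reader might infer that vital signs and ECG always require a change from baseline, so that its absence from Appendix 2 must be an oversight. The documents do not support that. Appendix 1 states for its two orthostatic rows that baseline is disregarded, and the QTcF row of Appendix 3 shows no change value, although that column is cut off in the available text. Appendix 2 itself mixes both kinds of criterion. What can be said is that 9.3 is silent where 9.4 and 9.6 refer to post-baseline visits.

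A simpler remedy, dropping baseline-flagged participants from the count, meets a fair objection: someone who enters at 1,450/mm³ and falls to 600/mm³ on treatment would disappear from the summary.

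**Conclusion.** The point holds at low priority. The overlap for haemoglobin and neutrophils follows directly from the two sets of limits, as does the lack of any numeric entry limit for several other flagged tests. The laboratory counting rule has no baseline condition. Followed as written, the plan can place an unchanged, permitted value in CT-10.1.

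The size is 2 percentage points per participant and per test, assuming 50 are dosed. How many there would be is unknown and may be none. The women's haemoglobin band is narrow; the men's haemoglobin and neutrophil bands are wider. No efficacy endpoint or error rate is affected.

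A reader might go further and conclude that the SAP attributes these values to centanafadine, or that the laboratory incidences will be materially inflated. Neither is supported. The SAP makes no causal statement about CT-10.1, it is silent rather than explicit about screening values, and no document gives a prevalence.

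**What to change.** In SAP 9.3, with a cross-reference at Appendix 2, state three things:

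1. CT-10.1 uses only values obtained after the first dose (V4, V6 and unscheduled).
2. For each test, the incidence is the number of participants with a new-onset abnormality divided by the number whose baseline value did not meet the criterion.
3. Participants who already met the criterion at baseline appear in a separate row of CT-10.1, with their baseline and worst post-dose values in CT-10.3.1, so that worsening on treatment stays visible.

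The denominator statement in the opening text of SAP 9 needs a matching exception for laboratory tests. Entry limits and flag thresholds need not change.

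The cost is a short SAP edit and some programming on data already collected. The downside is one more row in the table and a denominator that varies by test.
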